Intravenous fluid therapy for the treatment of emergency department patients with migraine headache: a pilot randomized controlled trial

Abstract:

Headache is one of the most common reasons patients visit the emergency department (ED), with migraines accounting for over one million annual US ED visits. While intravenous fluid (IVF) has not been prospectively studied in migraine patients, there is evidence that intravascular volume status affects central pain processing, and dehydration can trigger migraines. We propose a pilot, randomized controlled trial assessing the impact of an IVF bolus on patients with migraine headache. We hypothesize that patients who receive IVF will experience greater improvement in pain one hour after treatment as compared to controls. Adults treated in the Cooper ED with migraine headache will be randomized to receive normal saline at either 1000 ml/hr (treatment) or 10 ml/hr (control) for one hour, with a comparison in pain scores before and after treatment. Our first specific aim will establish the feasibility of successfully enrolling patients with migraine in the study and adhering to the study protocol. Our second specific aim will examine the efficacy of a normal saline bolus for relieving pain among patients with migraine headache. The data collected during this pilot study will support a competitive, larger-scale external grant application further investigating the efficacy of IVF for migraine.

Research plan

I. Project statement

Patients commonly present to the emergency department due to migraine headache. While some patients receive intravenous fluids as a method of controlling pain, the effectiveness of this intervention has not been prospectively studied. Our long-term objective is to determine the effect of an intravenous fluid bolus on pain among patients treated in the emergency department for migraine headache. The purpose of this pilot study is to obtain feasibility and preliminary outcome data in support of a future trial.

II. Specific aims

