Hypothesis 1: The proposed RCT protocol is feasible. Specific Aims

- **1a.** To determine whether the proposed study protocol can successfully recruit at least 75% of eligible patients.
- **1b.** To assess the ability of the proposed protocol to successfully blind participants to their intervention group, such that fewer than half of participants correctly identify their treatment arm.
- **1c**. To test the ability of the proposed protocol to successfully obtain patient follow-up at one hour, two hours, and 48 hours in at least 85% of participants.

Hypothesis 2: IVF administration will result in reduced pain scores in the ED and at follow-up. Specific Aims

1a. To test the efficacy of IVF in achieving an improvement in reported pain (0-10 scale) of at least 1.3 (minimally significant pain difference) as compared to controls between time 0 and one hour.

The proposed study constitutes a critical first step in demonstrating the potential feasibility and value of performing a large-scale RCT evaluating the potential efficacy of IVF administration for individuals presenting to the ED with migraine headache. This study will collect the necessary data to advance to initial stage NIH (R03, R21, R34) or PCORI funding.

III. Research strategy

A) Significance

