Participants will be English-speaking patients aged 18 or older, treated in the Cooper Hospital ED with a headache meeting ICHD-3 criteria for migraine. Patients will be excluded if in the opinion of the treating physician IVF administration is definitively indicated (ie. intractable vomiting, severe dehydration) or contraindicated (e.g. exacerbation of congestive heart failure).

Research assistants who are trained to identify potential clinical study participants and assess their eligibility for study enrollment are available in the ED from 8:30 am until 10:30 pm, 7 days per week to screen patients for inclusion.

2. Interventions

No previous trials have prospectively studied an IVF bolus for adults with migraine, limiting data on which to make dosing decisions. However, several trials have assessed the impact of IVF on postoperative nausea and vomiting and post-operative opioid requirements. One compared 15 ml/kg (mean total intervention dose of 1215 ml) with 2 ml/kg (mean dose 226 ml) of crystalloid solution before induction of anesthesia for minor surgery, finding a substantial reduction in post-operative nausea and vomiting, along with trends toward lower post-operative opioid requirements.³² Two additional small trials showed that for patients undergoing gynecologic procedures a 1000 ml crystalloid bolus resulted in improved post-operative nausea and vomiting compared with controls.^{33, 34} Finally, another trial comparing a control group of 2 ml/kg crystalloid to 12 ml/kg crystalloid solution or 12 ml/kg colloid solution showed improved post-operative nausea and vomiting among the two experimental arms. 35 In addition to these results showing efficacy with doses of approximately 1000 ml, clinical experience suggests that a dose of 1000 ml is commonly selected by ED physicians when treating patients with migraine, making this dose relevant to current clinical practice. Finally, a dose of 1000 ml limits opportunities for unblinding by avoiding administration of more than one bag of IVF. Based on these considerations, we plan to study the efficacy of a 1000 ml normal saline bolus versus control. In order to maximize the generalizability of our results, we will not restrict the use of additional interventions by ED providers.

Patients will be randomly allocated between two arms:

Patients in the intervention arm ("IVF group") will have a peripheral IV line placed by ED staff, and will receive 1000 ml of 0.9% normal saline bolus over one hour.

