follow-up will occur over the telephone. During this follow up assessment we will ask participants about their current pain, any recurrence of pain since leaving the hospital, current functional status, ability to tolerate oral intake, and adverse effects potentially related to the study intervention, including pain at the IV site, symptoms of thrombophlebitis, or peripheral edema. Global assessment of treatment is a function of both efficacy and tolerability, and will also be assessed by asking patients "The next time you visit the ED with a headache, would you wish to receive the same IV fluid treatment again?"

5. Outcomes

The primary outcome will be the difference in pain rating (0-10) between the start of the study intervention and one hour later, at completion of the intervention. The minimum clinically significant difference between treatment groups on the 0-10 verbal scale is 1.3. 36, 38, 39

Secondary outcomes will include:

Percentage of patients in each group who are pain-free two hours after initiation of the study intervention. This outcome is recommended for study by the International Headache Society.³⁷

Difference in verbal pain scale between start and two hours.

Global assessment of treatment, as described above.

Functional disability at one and two hours as compared to the start of treatment.

6. Analysis

We performed our sample size calculation with the understanding that the primary goal of this pilot study is to demonstrate the feasibility of the study protocol so as to inform a subsequent larger-scale trial.⁴⁰ The sample size calculation assumes a normal distribution. A sample size of 50 patients will provide the ability to detect a protocol adherence rate of 85% (+/- 10%) at a confidence level of 95%. In 2015, the Cooper ED treated over 300 patients who were diagnosed with migraine headache, suggesting that a goal of 50 participants over the 10 month active-enrollment period is attainable.

Using an intention-to-treat analysis, the primary outcome will be analyzed by calculating the mean change in pain scale within each study group, as well as 95% confidence intervals surrounding these point estimates.

IV. Expected outcome

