We anticipate that the results from this study will demonstrate the feasibility of identifying and enrolling ED patients with migraine headache, completing the study protocol, and obtaining outcome data including post-discharge follow-up assessments. We will determine the success of blinding both participants and outcome assessors to the study intervention. This study will also provide preliminary

outcome data regarding the use of an IVF bolus for the treatment of migraine headache. These pilot data will be used to support a future grant application for a larger study which will be appropriately powered to determine the efficacy of this intervention.

References

- 3. Bird S, Derry S and Moore RA. Zolmitriptan for acute migraine attacks in adults. *Cochrane Database Syst Rev.* 2014; 5: CD008616.
- 4. Singh A, Alter HJ and Zaia B. Does the addition of dexamethasone to standard therapy for acute migraine headache decrease the incidence of recurrent headache for patients treated in the emergency department? A meta-analysis and systematic review of the literature. *Acad Emerg Med.* 2008; 15: 1223-33.
- 8. Hoppe JA, Kim H and Heard K. Association of emergency department opioid initiation with recurrent opioid use. *Ann Emerg Med.* 2015; 65: 493-9 e4.

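### The primary outcome is analysed only as a mean change within each arm; the IVF-versus-control difference that the hypothesis, the efficacy aim and the 1.3-point threshold concern is never specified

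*Combined protocol and SAP*

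**What the plan says.** The question the trial sets itself is comparative in three places.

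- Abstract: "We hypothesize that patients who receive IVF will experience greater improvement in pain one hour after treatment as compared to controls".
- Section II, aim 1a under Hypothesis 2 (a different aim 1a, on recruitment, stands under Hypothesis 1): "To test the efficacy of IVF in achieving an improvement in reported pain (0-10 scale) of at least 1.3", and this "as compared to controls between time 0 and one hour".
- Section III.C.5, Outcomes: "The minimum clinically significant difference between treatment groups on the 0-10 verbal scale is 1.3".

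The analysis is not comparative. Section III.C.6 contains one sentence on the primary outcome. Under intention to treat, "the primary outcome will be analyzed by calculating the mean change in pain scale within each study group". The only intervals it promises are 95% CIs for those two arm means. The abstract likewise describes the comparison only as pain before against pain after treatment. No section gives a between-arm difference, an interval for one, a test or a model.

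Two further statements bear on the point. Section III.C.2 says that "we will not restrict the use of additional interventions by ED providers". Section IV leaves efficacy to "a larger study which will be appropriately powered to determine the efficacy of this intervention".

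**The concern.** The plan names a specific estimator, and it does not answer the question asked. A mean change in the IVF arm cannot be set against a threshold defined as a difference between arms. Both arms could improve by more than 1.3 points with no effect of fluid at all, because each arm's change includes the natural course of the attack and whatever other treatment was given.

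Three things are at stake.

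- **Prespecification.** The contrast, its sign, its interval and the method behind it (equal or unequal variances, adjusted for baseline pain or not) stay open until the data have been seen.
- **Displayed uncertainty.** The intervals the plan will show are narrower than the interval for the IVF effect, so they do not directly show how imprecisely that effect is known.
- **Use of the pilot.** These data are meant to support a grant application for a larger efficacy trial, and the between-group estimate with its interval is the relevant preliminary efficacy figure.

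A smaller mismatch goes with this: the aim speaks of testing efficacy, while section IV defers the determination of efficacy to a later trial.

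**Working it through.** **The plan's own figure.** The total of 50 rests on precision around an 85% adherence rate, ±10 percentage points at 95% confidence:

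n = 1.96² × 0.85 × 0.15 / 0.10² = 48.98, rounded up to 49.

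At n = 50 the half-width is 9.9 percentage points. The figure reproduces, and the sample size is not in dispute. It has no bearing on the precision of a pain difference.

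**Inputs for the pain comparison**

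- Total of 50 patients (section III.C.6).
- Two arms, permuted blocks of 4 or 6 (section III.C.3). The allocation ratio is not stated; 1:1 is assumed, giving 25 per arm.
- SD of the 0-to-1-hour change: not stated. A range of 2.0 to 3.5 points is assumed, equal in both arms.
- Threshold of 1.3 points between groups (section III.C.5).
- Complete one-hour data, relaxed below.

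**Formulas**

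- Per-arm half-width = t(0.975, 24) × SD / √25, with t = 2.064.
- SE of the difference = SD × √(2/25).
- Half-width for the difference = t(0.975, 48) × SE, with t = 2.011.

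| SD of change | Per-arm half-width (reported under the plan) | SE of difference | Half-width for difference | 95% CI if the observed difference is 1.3 |
|---|---|---|---|---|
| 2.0 | 0.83 | 0.57 | 1.14 | 0.16 to 2.44 |
| 2.5 | 1.03 | 0.71 | 1.42 | −0.12 to 2.72 |
| 3.0 | 1.24 | 0.85 | 1.71 | −0.41 to 3.01 |
| 3.5 | 1.44 | 0.99 | 1.99 | −0.69 to 3.29 |

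**Ratio of widths.** 2.011 × √2 / 2.064 = 1.38, the same at every SD.

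**Where an observed 1.3 stops excluding zero.** Solve 2.011 × SD × √(2/25) = 1.3, which gives SD = 2.29. Above that, an observed difference equal to the threshold has an interval that includes zero. This is a reason to present the contrast as an estimate; it does not measure the harm of leaving the contrast out.

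**Incomplete follow-up.** Aim 1c targets at least 85%. With 42 of 50 patients (21 per arm), the half-widths for the difference become 1.25, 1.56, 1.87 and 2.18 at the same SDs.

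**Can the difference be recovered from what would be reported?** Yes. Each arm's SE is its half-width divided by t(0.975, n−1), and for independent arms SE(difference) = √(SE₁² + SE₂²). At SD 2.0, 0.83 / 2.064 = 0.40 per arm, and √(0.40² + 0.40²) = 0.57, which agrees with the table.

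**What happens if a reader compares the two intervals by eye.** At SD 2.0, non-overlap needs an observed difference of about 1.65 (twice the unrounded half-width of 0.826). The interval for the difference excludes zero from 1.14. Requiring non-overlap corresponds to a two-sided alpha of about 0.005, so this reading is too strict.

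**The case against.** The best defence is that this is a drafting gap in a feasibility pilot. The comparative intent is plain throughout, both randomised arms are reported side by side by intention to treat, the point difference is one subtraction, and its standard error can be rebuilt as shown. Section III.C.6 calls feasibility the primary goal and sizes the trial on adherence; section IV promises only preliminary outcome data. Per-arm means with intervals are a reasonable pilot summary and supply the SDs needed to size the next trial. Co-treatment distorts inference only if the IVF arm is read alone. Judging by overlap errs on the cautious side, so a false claim of benefit is not the likely result.

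Much of this stands. No information is lost, low power is excusable here, unrestricted co-treatment is a stated choice made for generalisability, and the overlap reading is conservative. The figures also depend on an SD, an allocation ratio and complete data that the plan does not state.

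It does not remove the mismatch. The plan is not silent on the analysis; it names an estimator, and that estimator is within-arm. A declared primary outcome with a declared between-group threshold needs its contrast and interval written down beforehand, and a pilot can do that without claiming power. These arguments reduce the weight of the point. The wording of the aim (testing or estimating) is secondary and adds no weight of its own.

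**Conclusion.** The concern holds, with high confidence. The only analysis stated for the primary outcome does not estimate the quantity that the hypothesis, the efficacy aim and the 1.3-point threshold refer to. With 25 per arm and SDs of 2.0 to 3.5 assumed, the intervals to be reported (±0.83 to ±1.44) understate the uncertainty about the IVF effect (±1.14 to ±1.99) by a factor of about 1.38. The factor does not depend on the SD, but it does rest on equal arms of 25 and equal SDs. The conclusion that the contrast is missing rests on the text alone and needs none of these assumptions. Because the difference can be reconstructed and the trial is a feasibility pilot, this is something that should be fixed. It is not a flaw in the sample size or a threat to the trial's validity.

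**What to change.** Replace the primary-outcome sentence in section III.C.6 with text such as:

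> The primary outcome will be analysed by intention to treat as the between-group difference (IVF minus control) in mean pain reduction, where reduction is the time 0 score minus the one-hour score, so that positive values favour IVF. The difference will be given with its two-sided 95% CI and reported alongside the 1.3-point threshold as preliminary estimation, not as a powered test. Within-group means and their CIs are descriptive.

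The same text should say whether equal variances are assumed and whether the estimate is adjusted for baseline pain.

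Reword aim 1a under Hypothesis 2 so that it estimates the between-group difference in pain reduction with a 95% CI, in place of testing efficacy. That brings it into line with section IV.

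The cost is a few sentences of analysis text and one reworded aim. No new data, patients or visits are needed.

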Patients in the control arm ("control group") will have a peripheral IV line placed by ED staff, and will have a 1000 ml bag of 0.9% normal saline attached to the IV line, but the IV pump will be programmed to infuse 10 ml of fluid over one hour.

3. Allocation and blinding

We will randomize patients in permuted blocks of 4 or 6. Study assignments will be made through the use of sequentially numbered, opaque, sealed envelopes. Following enrollment, the nurse -- who will remain un-blinded -- will open the envelope and initiate the assigned intervention. An opaque cover will be placed over the IV pump, fluid bag, and drip chamber to maintain blinding of the patient, treating physician, and outcome assessor. Following completion of the intervention, in order to evaluate the success of blinding, patients and outcome assessors will be asked which treatment group they think was assigned.

4. Data collection

Research assistants will collect demographic information from patients, including age, sex, race, ethnicity, pre-existing comorbid conditions, and headache history.

We will assess pain at time 0 (start of the intervention), one hour (end of the intervention), and two hours using both a categorical scale (none, mild, moderate, or severe) and an 11 point verbal pain scale ranging from 0 (no pain) to 10 (worst pain imaginable), which has been validated for use in the ED setting.³⁶

Functional disability will be assessed before treatment, at one hour, and two hours. As recommended by the International Headache Society,³⁷ patients will describe their functional disability due to headache as none, mild (able to perform all activities of daily living, but with some difficulty), moderate (unable to perform some activities of daily living), and severe (unable to perform most activities or requiring bed rest).

We will measure adverse effects of treatment, including pain at the IV site by asking participants to rate the pain associated with IV insertion, as well as IV site pain at one and two hours.

Research assistants will record visit characteristics, including the timing of medications administered, need for rescue medication, opioid use, length of stay in the ED, and ED disposition (discharged, observation, admission).

Research assistants will contact participants 48 hours after they leave the ED. It is anticipated that the substantial majority of patients will have been discharged from the hospital, in which case

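### The primary pain analysis gives only unadjusted within-group mean changes: no between-arm estimate is planned, and the time-0 rating already collected is not used as a covariate

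*Combined protocol and SAP*

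**What the plan says.** III.C.5 (Outcomes) defines the endpoint: "The primary outcome will be the difference in pain rating (0-10) between the start of the study intervention and one hour later". It also sets the yardstick: "The minimum clinically significant difference between treatment groups on the 0-10 verbal scale is 1.3".

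III.C.6 (Analysis) gives the whole analysis of that endpoint in one sentence. By intention to treat, "the primary outcome will be analyzed by calculating the mean change in pain scale within each study group". Uncertainty is dealt with only in the closing clause of that sentence: "as well as 95% confidence intervals surrounding these point estimates". The point estimates are the two group means. The sentence contains no difference between groups, no interval for one, no test, no model and no covariate, and none of these appears elsewhere in the document.

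The aim under Hypothesis 2 (section II) is nevertheless comparative: an improvement of at least 1.3 points relative to controls from time 0 to one hour.

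The baseline value will be available, because III.C.4 (Data collection) says "We will assess pain at time 0 (start of the intervention), one hour (end of the intervention), and two hours". Allocation does not balance it. III.C.3 says "We will randomize patients in permuted blocks of 4 or 6" and names no stratification factor, and the eligibility criteria in III.C.1 set no pain threshold.

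**The concern.** There are two gaps in the same sentence.

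The first is that the plan produces two separate means with two separate intervals, while the aim needs one contrast. A reader who wants the effect of fluid will subtract one mean change from the other. That gives an unadjusted change-score contrast for which the plan provides no interval.

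The second concerns that contrast. A change score assumes that each extra point of baseline pain carries over as a full point at one hour. On a bounded 0-10 scale, patients who start higher have more room to fall, so the slope of the one-hour score on the time-0 score is often below 1. Subtracting the full baseline then over-corrects, and the arm that happened to start with more pain looks better. With a small sample and no stratification on pain, such an imbalance can be sizeable. ANCOVA estimates the slope from the data instead of fixing it at 1.

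At stake is the precision of the preliminary pain estimate that is meant to support a larger trial, and its sensitivity to chance imbalance.

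**Working it through.** **The plan's own figure.** The total is justified by "protocol adherence rate of 85% (+/- 10%) at a confidence level of 95" percent. The precision formula gives n = 1.96² × 0.85 × 0.15 / 0.10² = 48.98, rounded up to 49. With 50 patients the half-width is 1.96 × √(0.85 × 0.15 / 50) = 0.099, or 9.9 percentage points. The figure reproduces. It concerns adherence and says nothing about the pain outcome.

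**Inputs for the pain outcome.**
- From the documents: 50 patients, two arms, 95% intervals, a 1.3-point difference.
- Inferred: about 25 per arm. The allocation ratio is not stated.
- Assumed, because the documents give no values: SD at time 0 (s0), SD at one hour (s1), and the correlation between the two ratings (r, 0.3 to 0.7). Three SD pairs are used: 2.5/2.5, 2.0/2.5 and 1.7/2.7.

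**Formulas.**
- Variance of a change score: s0² + s1² - 2·r·s0·s1.
- Residual variance under ANCOVA: s1²·(1 - r²).
- 95% half-width for the arm difference: t × √(2 × variance / 25). For the change score, t = 2.011 on 48 degrees of freedom. For ANCOVA, t = 2.012 on 47, with a further factor √(1 + 1/46) = 1.011 for estimating the slope.
- Slope: r·s1/s0.
- SD of the chance difference in mean baseline pain: s0·√(2/25), which is 0.71, 0.57 and 0.48 for the three values of s0.
- Shift in the change-score contrast: (1 - slope) × imbalance.

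**Worked case, SDs 2.5/2.5, r = 0.3.** The change-score variance is 6.25 + 6.25 - 3.75 = 8.75, so the half-width is 2.011 × √(2 × 8.75 / 25) = 1.68. The ANCOVA variance is 6.25 × 0.91 = 5.69, so the half-width is 2.012 × 1.011 × √(2 × 5.69 / 25) = 1.37. A 1-SD imbalance shifts the contrast by 0.70 × 0.71 = 0.49 point.

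**All cases** (half-widths and shifts in points).

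| s0 / s1 | r | Slope | Half-width, change score | Half-width, ANCOVA | Shift at 1-SD imbalance | Shift at 2-SD imbalance |
|---|---|---|---|---|---|---|
| 2.5 / 2.5 | 0.3 | 0.30 | 1.68 | 1.37 | 0.49 | 0.99 |
| 2.5 / 2.5 | 0.5 | 0.50 | 1.42 | 1.25 | 0.35 | 0.71 |
| 2.5 / 2.5 | 0.7 | 0.70 | 1.10 | 1.03 | 0.21 | 0.42 |
| 2.0 / 2.5 | 0.3 | 0.38 | 1.53 | 1.37 | 0.35 | 0.71 |
| 2.0 / 2.5 | 0.5 | 0.63 | 1.30 | 1.25 | 0.21 | 0.42 |
| 2.0 / 2.5 | 0.7 | 0.88 | 1.025 | 1.027 | 0.07 | 0.14 |
| 1.7 / 2.7 | 0.3 | 0.48 | 1.55 | 1.48 | 0.25 | 0.50 |
| 1.7 / 2.7 | 0.5 | 0.79 | 1.345 | 1.345 | 0.10 | 0.20 |
| 1.7 / 2.7 | 0.7 | 1.11 | 1.10 | 1.11 | -0.05 | -0.11 |

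A positive shift favours the arm that started with more pain. In the last row the slope exceeds 1 and the direction reverses.

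A simulation of 10,000 trials per correlation at SDs 2.5/2.5 gave half-widths of 1.67 against 1.36, 1.41 against 1.24 and 1.10 against 1.02 for r = 0.3, 0.5 and 0.7, in agreement with the formulas.

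**In patients.** At SDs 2.5/2.5, 50 patients analysed by ANCOVA are worth about 75 (r = 0.3) or 65 (r = 0.5) analysed by change score, after the cost of estimating the slope.

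**The case against.** The strongest reply is that this is a feasibility pilot. III.C.6 says so, the 50 patients are sized on adherence, and section IV leaves efficacy to a later, adequately powered study. No test or progression rule depends on the pain estimate, and the within-group intervals already let a planner recover the SD of change. This stands as a limit on weight. It does not remove the point, because the pain change is the named primary outcome, the comparison with controls is a stated aim, and the pilot data are meant to support the next application.

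The second reply is that the size of the gain is entirely assumed. This also stands. Equal SDs with a low correlation is the most favourable case for adjustment. At 2.0/2.5 with r = 0.7, or 1.7/2.7 with r = 0.5, there is no gain.

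A reader might go further and infer three things that the documents do not support:
- That baseline pain is ignored. It is not: a change score subtracts it. What is missing is covariate adjustment, and only (1 - slope) of an imbalance remains.
- That the planned measure is biased. Randomisation keeps the difference in mean change unbiased on average; the error is conditional on the imbalance that happens to occur.
- That every estimate built on change scores is noisier than it need be. That depends on SDs and a correlation that the documents do not give, and the table includes cases where it is false.

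**Conclusion.** The point holds as an inexpensive improvement that should be made; it does not invalidate the trial. The part that needs no assumption is that III.C.6 plans neither a between-arm estimate nor covariate adjustment, while section II asks for a comparison with controls. The missing contrast is the more basic of the two gaps; the choice between ANCOVA and a difference in mean change is a question of efficiency.

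The size of the second gap rests on the assumed SDs and correlations and on the inferred 25 per arm. Across those cases the effect of ANCOVA on the half-width runs from about 18% narrower to under 1% wider. The possible gain is useful and the possible loss negligible. The shift left by chance imbalance is at most about 0.5 point for a typical (1-SD) imbalance. The 1.0-point figure belongs to a 2-SD imbalance, which arises in roughly 5% of trials, and should not be read as the expected effect.

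**What to change.** In III.C.6, state that the between-arm difference in one-hour pain, with its 95% CI, is estimated by a linear model for the one-hour score with treatment arm and the time-0 score as covariate, and that this is the reported primary pain estimate. Use the same model for the two-hour pain score. Keep the unadjusted mean change within each group, with its interval, as description.

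Write this in before outcome data are seen, so that the choice to adjust cannot follow from the imbalance observed. The cost is one sentence and one degree of freedom. No new data are needed and nothing in the conduct of the trial changes.
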